#### **PD Medication Reconciliation:**

The Principal Investigator (PI) and Transitions of Care (TC) Pharmacists (sub-investigator(s)) will complete the admission medication reconciliation.

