## **Prospective Study Period**

Data collection starting after completion of the Parkinson's Disease Inpatient Clinical Knowledge and Management Program for staff nurses, advanced practice nurses (APN), nursing assistants, patient care technicians, case managers, adult inpatient physician assistants, pharmacists, occupational therapists, physical therapists, nurse educators, and dietitians.

- Data will be extracted from EPIC and WatchRx records from the Watch Rx Web Interface.

Data collected from the automatic dispensing cabinet barcoding database will verify accuracy and timeliness of medication.

- Unstructured data will be collected by the principle investigator (PI), designees inclusive of study staff through focused chart review on 150 patients.
- Data will be analyzed for objectives and endpoints.

This data will compare prevalence of medication errors, complications associated with administration of contraindicated medications and timing of medications, falls and falls with

injury, positive CAM and Mini-Cog Scores, length of stay and cost per case in the study population. This phase will also assess the knowledge of the clinicians regarding the basic aspects of Parkinson's Disease inpatient management, the Parkinson's Disease Inpatient Clinical Knowledge and management program and integration of the smartwatch into the PD medication management.

- Parkinson's Disease Knowledge Assessment Survey (Appendix A)
- Parkinson's Disease Inpatient Clinical Knowledge and Management Program (Appendix B)

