#### **WatchRx System Enrollment:**

Using Internet Explorer web browser, the Principal Investigator and the TC Pharmacist (sub investigator(s) will complete the following:

- Enter the patient's information into the WatchRx Inc. Website interface to create the patient profile and PD medication regimen
- Register the patient into WatchRx web interface via website URL by entering the PD patient's name, unit number and room number.

- Enter the patient PD medication administration schedule as ordered
- Assign the WatchRx Smartwatch to the patient
- Review the WatchRx Smartwatch functions with the patient
- Review the Aware in Care Kit with the PD patient

The primary nurse will be asked to wear the WatchRx smartwatch. After obtaining verbal consent, the Principal Investigator and TC Pharmacist will review the patient's PD medication schedule in WatchRx smartwatch with the primary nurse.

The WatchRx web interface will activate reminder alerts from the patient's WatchRx Smartwatch to the primary nurse WatchRx smartwatch. Alerts reminders will send fifteen minutes before the PD medication is due. Medication reminder alerts will continue to be sent from WatchRx smartwatch worn by the patient to the WatchRx Smartwatch worn by primary nurse at 3-minute intervals for a period of 10 minutes or until the PD medication is administered.

At each end-of-shift and/or at handoff, the WatchRx smartwatch will be cleaned using Super SaniClothTM and the nurses will document completion of the WatchRx smartwatch cleaning procedure on the WatchRx Smartwatch cleaning log and verify by signing their names (Appendix F).

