## Measurements

The following will be documented on a case report form: demographics (age, sex, and race), comorbidities and complications, date of discharge, length of stay, and number of medication discrepancies.

- Subject ID (coded de-identified patient identifier)
- Demographics (age race, gender)
- Primary Diagnosis
- Comorbidities
- Medication list at admission (Admission Medication Reconciliation)
  - Number of medications at admission
- Prescribed Medication List (Medication Administration Record)
  - Number of medications during hospitalization
- Medication list at discharge (Discharge Medication Reconciliation)
- Complications associated with medication administration
- Medication Administration Schedule
  - Order Time
  - Patient Falls
  - Number of falls
  - Time of patient falls
  - Injury
- Length of Stay

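### Judgement-based patient outcomes are open to unmasked and unequal ascertainment: the PI delivers the intervention and abstracts charts, attribution has no rule, and chart review is described for one phase only

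*Combined protocol and SAP*

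**What the plan says.** **Delivery.** Under PD Medication Reconciliation: "The Principal Investigator (PI) and Transitions of Care (TC) Pharmacists (sub-investigator(s)) will complete the admission medication reconciliation". Under WatchRx System Enrollment, "the Principal Investigator and the TC Pharmacist (sub investigator(s) will complete the following", a list that covers entering the schedule and includes "Assign the WatchRx Smartwatch to the patient". Later in that section, "the Principal Investigator and TC Pharmacist will review the patient's PD medication schedule in WatchRx smartwatch with the primary nurse".

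**Abstraction.** Under Prospective Study Period: "Unstructured data will be collected by the principle investigator (PI), designees inclusive of study staff through focused chart review on 150 patients". Nothing in the available text keeps the people who deliver the intervention apart from those who abstract outcomes. There is also no masked abstractor, adjudication or agreement check.

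**Items that need judgement.** The same section lists among the compared outcomes "complications associated with administration of contraindicated medications and timing of medications". The case report form under Measurements includes "Complications associated with medication administration" and "number of medication discrepancies". None of these is defined, and no rule says when a complication counts as associated with a drug or its timing.

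**Sources by phase.** The Retrospective Study Period section describes EPIC reports produced by business intelligence, plus dispensing-cabinet barcoding data. The Prospective Study Period section describes EPIC, WatchRx records, barcoding data and the focused chart review. Barcoding is to verify medication accuracy and timeliness in both phases.

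**The concern.** The patient comparison is non-randomised, 2015 against a later period, and Data Analysis plans only simple group tests. Any difference in how events are found or classified between phases passes straight into the result, and no planned analysis could detect it.

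Two features of the plan can create such a difference. First, the PI may decide whether a complication in a patient whose medication list and watch the PI set up was due to medication. That decision is unmasked and has no written rule. Second, free-text review is described for prospective patients only, so an event recorded only in notes can be found in one phase and missed in the other.

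At stake is the credibility of the attributed-complication comparison, and of medication error and discrepancy counts to the extent that they come from chart review.

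**Working it through.** **1. Who does what.**

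| Task | Role named | Section |
|---|---|---|
| Admission reconciliation | PI, TC pharmacists | PD Medication Reconciliation |
| Schedule entry, watch assignment, nurse briefing | PI, TC pharmacist | WatchRx System Enrollment |
| Free-text chart review, 150 patients | PI, designees including study staff | Prospective Study Period |

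For the PI the overlap is explicit. For the TC pharmacists it is only possible: they are sub-investigators and could serve as designees.

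**2. Which outcomes are exposed.**

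| Item | Source or definition given | Exposure |
|---|---|---|
| Knowledge score (primary) | Clinician test | None |
| Length of stay | EPIC | Little |
| Administration timing | Barcoding, both phases | Little |
| Positive confusion and delirium scores | Standardised examinations (Mini-Cog, CAM) | No causal call needed |
| Medication errors (secondary) | Not defined; barcoding verifies accuracy | Only the part taken from chart review |
| Medication discrepancies (form item) | Not defined; counter not named | Open |
| Attributed complications (compared outcome and form item) | No rule | Open |

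**3. Size.** The plan states no alpha, power, event rate or effect size, so it has no figure to reproduce. The following is an illustration.

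From the documents: 150 patients per phase. Assumed: two-sided alpha 0.05; the same true complication rate p in both phases; one phase records all events and the other a share s of them.

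With p1 = p, p2 = s × p and p̄ = (p1 + p2)/2:

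- SE0 = √[p̄(1 − p̄) × 2/150]
- SE1 = √{[p1(1 − p1) + p2(1 − p2)]/150}
- chance of a significant result in the biased direction = Φ[(p1 − p2 − 1.96 × SE0)/SE1]

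Example, p = 0.30 and s = 0.8: p2 = 0.24, p̄ = 0.27, SE0 = 0.0513, SE1 = 0.0511. Then (0.06 − 1.96 × 0.0513)/0.0511 = −0.79, and Φ = 0.214.

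| Share recorded, s | p = 10% | p = 20% | p = 30% | p = 40% |
|---|---|---|---|---|
| 0.9 | 4.8% | 6.4% | 8.3% | 10.6% |
| 0.8 | 8.8% | 14.5% | 21.4% | 30.2% |
| 0.7 | 15.2% | 28.1% | 43.1% | 59.3% |

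With equal recording the figure is 2.5% in each direction.

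**4. Direction.** The formula is symmetric in the two phases. If the prospective abstractor under-calls, the table gives the chance of a false finding for the intervention. If the 2015 reports miss events that chart review would have found, the same table gives the chance of a false finding against it. If both happen to the same degree, they cancel.

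**5. Counts.** For a count outcome, assume a true mean of 2 events per patient and a share u fewer recorded in one phase. Then z = 2u/√{[2k + 2(1 − u)k]/150}, where k is the variance-to-mean ratio. For u = 0.10, 0.15 and 0.20, a false two-sided difference occurs 24%, 48% and 73% of the time with k = 1, and 14%, 27% and 45% with k = 2. The mean and the shares are assumptions. For medication errors, the barcoding check would reduce u by an amount the documents do not allow one to estimate.

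**The case against.** The strongest case on the other side has four parts.

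- **Barcoding verifies medication accuracy and timeliness in both phases.** This stands. It protects timing and part of the error count. It cannot decide whether a fall or confusion was due to a drug, so attributed complications are not covered.
- **The clearest judgement items are not listed endpoints.** This also stands. Attributed complications and discrepancies are absent from Secondary Endpoints, and Hypothesis defines complications by a list that needs no causal call. The exposure is therefore narrow, but Prospective Study Period does say that attributed complications will be compared.
- **The size rests on assumed inputs.** True. The tables show sensitivity and are not an estimate for this study.
- **Masking to phase is not practical, because chart dates reveal it.** Also true. An abstractor who did not deliver care to that patient removes one source of expectation, but not knowledge of the phase.

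A reader might infer something stronger: that the investigators' leniency will make the intervention look better. The documents do not support this. Chart review is described for the prospective phase only, so fuller ascertainment could raise prospective counts. Careful reconciliation could likewise yield more recorded discrepancies. Nor do the documents say that the reconciler counts those discrepancies, or that the TC pharmacists abstract charts.

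**Conclusion.** The concern holds in limited form. As written, the plan lets the PI both deliver the intervention and make unmasked causal calls on the same patients without a rule, and it describes chart review in one phase only. Attributed complications are exposed, as are medication errors and discrepancies so far as they rest on chart review.

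The bias has unknown direction and size. Under the assumptions shown, 80% recording in one phase raises the one-directional false-positive chance from 2.5% to between 9% and 30%, and 90% recording raises it to between 5% and 11%. The primary endpoint is untouched, and length of stay and barcode-verified timing are little affected. The change is worth making because it is cheap, but it does not bear on the study's main result.

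**What to change.** 1. **Prospective Study Period:** state that free-text data for a patient are abstracted by an existing designee who did not reconcile medications, enrol or set up the watch for that patient.
2. **Prospective Study Period and Measurements:** have the abstractor record only the event, the drug and the times. Either drop the attribution to medication, or derive it by one prespecified time rule programmed in SAS and applied to both phases.
3. **Data Analysis:** base between-phase comparisons on data elements obtained from the same source in both phases (EPIC and barcoding). Report items available only from prospective chart review descriptively. If chart review of the 2015 patients was also intended, say so and describe it.
4. **Limitations:** add that abstractors are not masked to phase.

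**Cost:** some scheduling effort among staff the plan already allows for, changes to form wording, loss of the abstractor's causal impression, and no between-phase test for items found only by chart review. No new patients or staff are needed, and care does not change.

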#### **WatchRx System Enrollment:**

Using Internet Explorer web browser, the Principal Investigator and the TC Pharmacist (sub investigator(s) will complete the following:

- Enter the patient's information into the WatchRx Inc. Website interface to create the patient profile and PD medication regimen
- Register the patient into WatchRx web interface via website URL by entering the PD patient's name, unit number and room number.

- Enter the patient PD medication administration schedule as ordered
- Assign the WatchRx Smartwatch to the patient
- Review the WatchRx Smartwatch functions with the patient
- Review the Aware in Care Kit with the PD patient

The primary nurse will be asked to wear the WatchRx smartwatch. After obtaining verbal consent, the Principal Investigator and TC Pharmacist will review the patient's PD medication schedule in WatchRx smartwatch with the primary nurse.

The WatchRx web interface will activate reminder alerts from the patient's WatchRx Smartwatch to the primary nurse WatchRx smartwatch. Alerts reminders will send fifteen minutes before the PD medication is due. Medication reminder alerts will continue to be sent from WatchRx smartwatch worn by the patient to the WatchRx Smartwatch worn by primary nurse at 3-minute intervals for a period of 10 minutes or until the PD medication is administered.

At each end-of-shift and/or at handoff, the WatchRx smartwatch will be cleaned using Super SaniClothTM and the nurses will document completion of the WatchRx smartwatch cleaning procedure on the WatchRx Smartwatch cleaning log and verify by signing their names (Appendix F).

## **Sample Size Calculation**

A total of 433 patients were admitted to Hackensack University Medical Center with a diagnosis of PD in the year 2014. A convenience sample of 300 patients, 150 patients in the prospective phase and 150 patients in the retrospective phase, and approximately 346 clinicians, before and after implementing the Parkinson's Disease Inpatient Clinical Knowledge and Management education program will be enrolled in the study.

The sample of clinicians will include physician's assistant, advanced practice nurses, staff nurses, nurse educators, case managers, dietitians, pharmacists, physical therapist and occupational therapist. (Table 1)

Categories	Overall population	Sample population	Percentage (Sample size)
Staff Nurses Adult (Inpatient Units)	1931	100	5 %
Nursing Assistants	277	N/A	
Patient Care Technicians	165	N/A	
Advanced Practice Nurses (Adult Inpatient Units)	107	87	81%
Case Managers(Adult Inpatient Units)	48	48	100%
Nurse Educator Adult Inpatient	20	19	95%
Physician's Assistant Adult Inpatient	73	40	54%
Dietitians	17	17	100%
Pharmacists	119	12	11%
Physical Therapist	17	17	100%
Occupational Therapists	6	6	100%

Table 1

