## **Retrospective Study Period**

Version 5 Revised 5/9/2019

Data collection of adult patients admitted with a primary and secondary diagnosis of Parkinson's disease during January – June 2015.

- Data will be extracted from the EPIC (current EMR system at Hackensack University Medical Center).
- Business intelligence will run the data and create reports with the specific data points mentioned above prior to providing it to the study team for further statistical analysis.

Data collected from the automatic dispensing cabinet barcoding database will verify accuracy and timeliness of medication.

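### The 150 retrospective controls are a convenience sample with no selection rule, although an EPIC report on the January to June 2015 admissions would allow all eligible records or a random or consecutive set

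*Combined protocol and SAP*

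**What the plan says.** The Sample Size Calculation section describes the patients as "A convenience sample of 300 patients, 150 patients in the prospective phase and 150 patients in the retrospective phase". The label covers both phases. The section gives no power calculation for patients and does not say whether the retrospective records are all, consecutive or randomly chosen. It also supplies the only volume figure in the document: "A total of 433 patients were admitted to Hackensack University Medical Center with a diagnosis of PD in the year 2014".

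The Retrospective Study Period section describes the control group without a cap: "Data collection of adult patients admitted with a primary and secondary diagnosis of Parkinson's disease during January – June 2015". The source is EPIC, and "Business intelligence will run the data and create reports with the specific data points mentioned above prior to providing it to the study team". A second source is added: "Data collected from the automatic dispensing cabinet barcoding database will verify accuracy and timeliness of medication". No step is described at which records are picked. The one manual review with a number attached, "through focused chart review on 150 patients", stands under Prospective Study Period.

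The Limitations section lists convenience sampling but offers no remedy. The Data Analysis section plans two-group and multi-group tests without covariate adjustment.

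**The concern.** Convenience sampling is understandable for inpatients who must be approached and must consent. It is harder to justify for stored records whose list comes from an electronic report, because a take-all, consecutive or random rule is available there.

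If the report holds more than 150 eligible records, something has to decide which 150 are analysed, and under the convenience label nothing controls that choice. If the choice is related to length of stay, falls, confusion, delirium or medication timing, the control mean or rate for that endpoint shifts. With unadjusted tests, the shift passes straight into the comparison of phases. The retrospective group is the comparator for the patient-level secondary endpoints. The primary endpoint, clinician knowledge, is not affected.

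**Working it through.** **Inputs.** From Sample Size Calculation: 150 retrospective and 150 prospective patients, and 433 patients with PD in 2014. From Retrospective Study Period: a window of six months (181 days) in 2015. The documents do not give the number of 2015 records, the share that is eligible, or any alpha, power, effect size, SD or event rate for the patient endpoints.

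**1. The plan's own figure.** 150 + 150 = 300, as stated. With no design assumptions given, 150 per phase cannot be derived from a formula.

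**2. Records in the window (assumes 2015 resembled 2014).** 433 × 6/12 = 216.5; by days, 433 × 181/365 = 214.7. This is before any eligibility filter.

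**3. Share omitted.** With N eligible records, the omitted share is 1 − 150/N, or zero if N is 150 or fewer. The last column is the standard error of a difference in means with all N controls, divided by that with 150: √[(1/150 + 1/N) / (2/150)].

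| Eligible share of 216.5 (assumed) | N | Omitted share | SE ratio |
|---|---|---|---|
| 100% | 216.5 | 30.7% | 0.920 |
| 90% | 194.9 | 23.0% | 0.941 |
| 80% | 173.2 | 13.4% | 0.966 |
| 70% | 151.6 | 1.0% | 0.997 |
| 60% | 129.9 | 0% | not applicable (fewer than 150 exist) |

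The break-even is 150/216.5 = 69.3% eligible. At or below that share, 150 already takes every eligible record. If 2015 volume was higher, the share rises: N = 250 gives 1 − 150/250 = 40%.

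**4. Bias in the control mean.** Bias = (1 − 150/N) × D, where D is the mean of the kept records minus the mean of the omitted ones. D is unknown and may be zero. Illustrations at N = 216.5:
- D = 0.25 SD gives 0.307 × 0.25 = 0.08 SD.
- D = 0.5 SD gives 0.307 × 0.5 = 0.15 SD.
- D = 2 days of stay gives 0.307 × 2 = 0.6 day.
- For a rate, a 10-point difference gives 3.1 points.

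At 80% eligible, each would be multiplied by 0.134 instead of 0.307.

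**5. Precision.** In SD units, the standard error is √(1/150 + 1/150) = 0.1155 with 150 controls and √(1/216 + 1/150) = 0.1063 with 216. The ratio is 0.920, so intervals are about 8% narrower. Assuming two-sided alpha of 0.05, the difference detectable with 80% power falls from 0.323 to 0.298 SD, and power for 0.30 SD rises from 73.8% to 80.6%.

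**The case against.** The strongest reply is that the documents do not show any picking of charts. The Retrospective Study Period section can be read as a full extract, with 150 as the expected yield and the convenience label referring to site and window. That reading is possible, so this is a conflict to reconcile and a risk to close, not a demonstrated bias. It does not remove the point, because Sample Size Calculation names convenience sampling for these 150 records and no section states another rule. Listing it under Limitations discloses the choice but does not control it.

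Four stronger readings are tempting and are not supported:

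- **That 31% of the control data is discarded.** About 216 is a pro-rata of 2014 volume before eligibility. The omitted share could be zero.
- **That whoever chooses the records sees the outcomes.** The report goes to the study team with its data points, so this is not ruled out. But no section says who reduces the list to 150, when, or with what in view.
- **That a complete extract would remove selection bias from the comparison.** Prospective patients must consent and accept the watch, which cannot be applied to 2015 records. The calendar gap and unadjusted tests also remain. Taking every 2015 record without the chart-assessable criteria could widen the mismatch.
- **That using every record is free.** The documents give no cost. Dispensing-cabinet data must also be obtained, and the Measurements section lists items that may need abstraction, such as the medication lists.

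**Conclusion.** The plan names convenience sampling for a control group drawn from stored records, where a controlled method is available. Its two descriptions of that group do not agree on whether any selection takes place. If 2015 volume resembled 2014, the share of eligible records left out lies between 0% and about 31%, depending on eligibility; it would be larger if volume was higher. The resulting bias in the secondary-endpoint comparator equals that share times an unknown difference between kept and omitted records, and it arises only for endpoints related to the choice. The gain in precision is modest: at most about 8% on confidence-interval width at N of about 216, and about 3% at 80% eligible.

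**What to change.** For the retrospective phase, replace convenience sampling with all January to June 2015 records that meet the criteria assessable from the chart (for example age, diagnosis, orientation and infection status). If abstraction or dispensing-cabinet linkage limits the number to 150, draw a seeded random sample or a consecutive series from the EPIC list before outcomes are viewed. State the rule in both Sample Size Calculation and Retrospective Study Period so that the two agree. Report the number of records in the window, the number eligible and the number analysed.

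The cost is a few sentences in the plan. Using all records would add at most about 66 (216.5 − 150) under the 2014-volume assumption, with the abstraction or linkage work they need. A random or consecutive 150 adds essentially none. The consent, watch-acceptance and calendar-time differences between phases need separate handling.
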